5.5 Treatment assignment

This is an open label, non-randomized study. Subjects will be assigned to MT-3724 treatment either in one of the sequential dose cohorts (Part 1) or in the MTD expansion cohort (Part 2). MT-3724 treatment assignment may occur only after the investigator declares the subject

eligible and the medical monitor reviews the screening results and acknowledge the investigator's eligibility decision.

All subjects in all cohorts will receive the same standard dose of LEN ([Section 5.2](#)).

Assignment of screening slots and treatment slots will be done on the basis of competitive enrollment (i.e. "first-come first-served"). The details will be described in the standalone Cohort Management Plan.

5.6 Blinding

Not applicable; this is an open-label study.

5.7 Treatment compliance

MT-3724

Because MT-3724 is administered IV, treatment compliance will be monitored through the eCRF and source documents (subject notes and pharmacy records) and clinical observations during study drug infusion. Actual dosing schedule vs planned dosing schedule will be used to assess compliance. Details will be provided in the standalone Pharmacy Manual.

Lenalidomide

LEN tablets will be dispensed to subjects to be taken on an out-patient basis. LEN may also be administered to subjects during clinic visits. During the study the subjects will be instructed to document intake of LEN tablets in a diary by entering the date and time of dosing as well as the administered dose. Subjects will be instructed to return all packages of used and unused LEN to the study unit. Returned LEN tablets will be counted by the study center to evaluate treatment compliance. The data from the subject diary will be transferred into the eCRF to capture any dose delays and modifications. Any discrepancies between actual and expected amount of returned study medication must be discussed with the subject at the time of the visit and any explanation must be documented in the source records.

5.8 Treatment duration

In Part 1 and Part 2, the treatment with MT-3724 and/or LEN in this study may be continued until death, progressive disease, AE requiring discontinuation or withdrawal of consent, any other reason for study discontinuation, or until study discontinuation. Thereafter, the subject will undergo the EoT Visit and STFU phone call.

5.9 Prohibited treatment

The following treatments are not permitted during the study:

- All systemic treatments for NHL.
- Radiotherapy to tumor lesions that would be chosen as target lesions (measurable disease).

- Palliative radiotherapy to non-target lesions may be permitted (Section 5.10).
- Systemic immune modulators from C1D1 until the EoT Visit, unless used for a TEAE or as pre-medication for MT-3724.
 - The immune modulators include, but are not limited to, systemic corticosteroids at doses >20mg/day or prednisone equivalent for >1 week, cyclosporine and tacrolimus.
- Vaccines: Subjects should not receive any live vaccines from 4 weeks before the start of treatment until 28 days after the last dose of MT-3724, unless the investigator believes benefits outweigh risk, after approval by the sponsor.

5.10 Permitted medication

The use of G-CSF, GM-CSF, platelet and blood transfusions and concomitant medications is permitted during the treatment phase at the investigator's discretion for management of appropriate toxicities. In particular, G-CSF is required for the treatment of Grade 3 neutropenia.

Palliative therapy such as radiotherapy (which spares at least 50% of bone marrow producing regions) to non-target lesions or intrathecal chemotherapy is allowed at the investigator's discretion after consultation with the medical monitor. Please note: palliative therapy is not allowed up to 2 weeks of C1D1 through and not during the DLT assessment period (cycle 1).

While the use of certain immunomodulators is prohibited as described in [Section 5.9](#), the use of NSAIDs is permitted.

5.10.1 Reasons for caution

No results are available about the potential for drug-drug interactions between MT-3724 and LEN, or between MT-3724 and other drugs. Therefore, investigators should use caution when prescribing concomitant medications

6 STUDY ASSESSMENTS

Please refer to the schedule of assessments to see which assessments need to be performed at each visit ([Schedule of Assessments](#)).

Unscheduled visits may occur when indicated at the investigator's discretion. The results obtained at unscheduled visits should be entered into the eCRF (where applicable) and recorded in the source documentation.

All assessments will be performed by the investigator or medically qualified designee or other personnel at the investigating site.

6.1 General subject characteristics

6.1.1 Demographics

Information about date of birth/age, gender, race/ethnicity, detailed smoking history and alcohol history will be recorded during screening.

6.1.2 Body weight

Body weight (kg) will be measured at the following time points:

- At screening
- Pre-dose on each dosing day for MT-3724
- At the EoT Visit

The body weight measured before the start of MT-3724 dose C1D1 will be used to calculate the MT-3724 dose in all subsequent cycles. The dose must be re-calculated when the body weight has changed by >10% from the baseline value, or according to institutional policies should they require adjustment for any change in body weight.

All body weight measurements will contribute to the safety assessment. Unscheduled body weight measurements could be made for safety assessment at the investigator's discretion.

6.1.3 Height and BMI

Height in meters (m) and body mass index (BMI) will be measured at screening.

6.1.4 NHL assessment

The NHL assessment will be performed at screening by documenting the biopsy method by which the NHL histology and CD20 status has been confirmed at the initial diagnosis and at baseline.

The following information will be documented:

- NHL assessment (status at initial diagnosis):

- NHL type (histology)
- Staging (Ann Arbor Classification-Cotswold Modification)
- Grading (low, intermediate, high)
- NHL assessment (status at Screening)
 - NHL type [histology and CD20+ status confirmation by historical or fresh biopsy (bone marrow, lymph node, organ) in relapse or refractory setting]
 - Date of most recent relapse
 - Staging
 - Grading at relapse
 - Grading at screening
 - Time to first relapse
 - Mutational status (e.g., MYC and/or BCL2 and/or BCL6 rearrangement/overexpression; del 9p32, TP53, MLL2 mutations)
 - Molecular subtype (GCB vs ABC)

The prognostic assessment instruments (Ann Arbor Classification with Cotswold Modification and (follicular lymphoma) International Prognostic Index) are described in [Appendix 2](#).

6.1.5 Prior systemic therapy

Prior systemic therapy (including SCT and CAR-T) for NHL administered at any time before the start of treatment will be assessed. Each regimen (line of treatment) should be documented in sequential order of past use with the outcome of therapy. The start and stop dates of the regimen (i.e., line of treatment) should be recorded along with each individual agent given in the regimen. The date of the last CD20-based therapy should also be documented.

6.1.6 Prior radiotherapy

Prior radiotherapy for NHL administered at any time before the start of treatment will be assessed and documented at screening.

6.2 Safety assessments

Note that the AE are described in the [Section 6.3](#), and the laboratory safety tests are described together with all laboratory tests in the [Section 6.4](#) and [Appendix 1](#).

6.2.1 Medical history

Medical history will be recorded at screening. This will include prior surgery, prior and concomitant illnesses and allergy history. The prior antitumor chemotherapy, radiotherapy and tumor related biopsies or surgery will be collected and documented on a separate eCRF form.

Illnesses that occurred at any time before the start of screening that, in the investigator's opinion, could increase the risk to subject and/or influence the study endpoints should be captured in the medical history as prior illnesses. Those illnesses that are active at the time of informed consent will be regarded as concomitant illnesses.

New illnesses and/or worsening of concomitant illnesses detected by verbal probes or subject's spontaneous reports between the screening and the start of treatment should be reported medical history unless they are due to study-mandated procedures, in which case they should be reported as AEs.

6.2.2 Prior and concomitant medications

Any medication (both prescription and over-the-counter [OTC] medications and supplements, and palliative treatments such as radiation or intrathecal chemotherapy, when permitted), used within 4 weeks prior to the start of treatment until the STFU Visit will be recorded in the eCRF, together with the main reason for its prescription.

The medications taken before the start of treatment on C1D1 will be regarded as prior medications (prior NHL therapy will be captured separately, [Section 6.1.5](#)). The prior medications will be captured at the following time points:

- During the screening period
- Before the start of treatment on C1D1.

The medications taken after the start of treatment on C1D1 will be regarded as concomitant medications. Concomitant medications will be captured at all visits and telephone contacts from the start of treatment until the STFU Visit.

6.2.3 Physical examination (PE)

A PE will be performed by a physician or a qualified delegate at the investigating site.

The full PE will be performed at the following time points:

- At screening
- At the EoT Visit

Abbreviated PE:

- Before MT-3724 dose on D1 of each cycle

The investigator or delegate at the site will perform the PE and evaluate the results. The PE can be captured up to 24 hours before dosing and must be done before dosing is allowed. The overall PE result will be categorized as 'normal', 'abnormal, not clinically significant (NCS)', or 'abnormal, clinically significant (CS)'. Any abnormal CS result of the PE should be followed up at the investigator's discretion and reported as an AE in the electronic CRF

(eCRF). Comments about abnormal NCS result of the PE, either overall or for individual aspects or body parts, will not be collected in the eCRF.

Complete physical examination

At a minimum, the following aspects/body parts should be assessed during the complete PE:

- General appearance
- Skin (paleness, jaundice, redness/rash, acneiform changes)
- Extremities (petechial bleedings, ulcers, signs of thrombosis), hands and feet (signs of hand-foot syndrome/palmar-plantar erythrodysesthesia)
- Ears, eyes (jaundice, inflammation), nose and throat (presence of petechial bleedings, gingival bleeding)
- Head and neck
- Lungs
- Heart
- Abdomen (pain, tenderness, peristaltic, ascites, organomegaly)
- Lymph nodes
- Neurological examination to include the following assessments:
 - Oculomotor testing, pupil accommodation, double images
 - Motor system: muscle strength of arms
 - Sensory system: pain and touch sensation of thighs
 - Mental Status
 - Posture
 - Coordination: finger-to-nose and heel-to-shin test
 - Reflexes: biceps, patella and plantar (Babinski's sign) test
 - Gait: walking freely, on toes and on heels
 - Romberg test

Other aspects/body parts or organ systems may be assessed at the investigator's discretion.

Abbreviated physical examination

At a minimum, the following aspects/body parts should be assessed during the abbreviated PE:

- General appearance
- Skin (paleness, jaundice, redness/rash, acneiform changes)
- Ears, eyes (jaundice, inflammation) nose, throat (presence of petechial bleedings, gingival bleeding)
- Lungs
- Heart
- Abdomen (pain, tenderness, peristaltic, ascites, organomegaly)

- Lymph nodes
- Extremities (petechial bleedings, ulcers, signs of thrombosis), hands and feet (signs of hand-foot syndrome/palmar-plantar erythrodysesthesia)
- Abbreviated neurological examination to include the following assessments:
 - Oculomotor testing, pupil accommodation, double images
 - Motor system: muscle strength of arms
 - Sensory system: pain and touch sensation of thighs
 - Mental Status (awareness of self and environment)
 - Posture
 - Coordination: finger-to-nose and heel-to-shin test

Other aspects/body parts or organ systems may be assessed at the investigator's discretion.

6.2.4 Eastern Cooperative Oncology Group Performance Status

ECOG performance status will be done at the same timepoints as physical examination, see [Appendix 6](#).

6.2.5 New York Heart Association

NYHA classification will be performed at screening, see [Appendix 7](#) for subjects with heart failure.

6.2.6 Vital signs

Vital signs include blood pressure (BP), heart rate (HR), respiratory rate (RR), and body temperature (°F or °C). BP and HR will be measured after 5-10 minutes of quiet rest in a sitting or semi-recumbent position using an automatic (preferred) or manual BP measuring device.

Vital signs will be assessed at the following time points:

- At screening
- Before the start of each MT-3724 infusion in each cycle;
- At 0.5h, 1h and 2h (±10 min allowed at each time point) after the start of each MT-3724 infusion in each cycle
- At 3h and 4h (±10 min allowed at each time point) after the start of MT-3724 infusion on C1D1
- At the EoT Visit

Unscheduled VS measurements may be performed at investigator's discretion in each cycle.

Any clinically-significant abnormality in VS should be investigated by repeat assessments (number and timing at investigator's discretion). The confirmed clinically significant abnormalities should be reported as AE in the eCRF.

6.2.7 Left ventricular ejection fraction

Left ventricular ejection fraction assessment should be assessed by echocardiography (ECHO). If ECHO is not available or appropriate according to the institutional standard, then multi-gated acquisition (MUGA) scan is permitted. The same modality should be used throughout the study. Left ventricular ejection fraction will be assessed at the following time points:

- At screening (within 1 month before starting study treatment)
 - A pre-study LVEF assessment is acceptable if obtained within 6 months before screening and at least 28 days after the last cancer therapy provided the subject has not received any potentially cardiotoxic agents since then.
- At the EoT Visit (only if the subject has received MT-3724 in ≥ 3 cycles irrespective of the number of MT-3724 doses in each cycle).

6.2.8 Electrocardiograms

Standard resting 12-lead ECG assessments will be performed after the subject had rested rest quietly for 5-10 minutes in supine or semi-recumbent position. The ECG recordings will be obtained at the following time points:

- At screening (triplicate ECG, i.e. 3 ECG recordings obtained in close succession and not more than 2 minutes apart)
- Before the start of MT-3724 infusion on D1 of each cycle (single ECG recording will be performed)
- At the EoT Visit (single ECG)

If the ECG printout is of poor quality, additional ECG(s) may be obtained at the same time point until an ECG of adequate quality is obtained. Such additional ECG(s) do not have to be reported as unscheduled assessments.

When PK, ECG and VS assessments are scheduled to occur at the same time point, the ECG and VS should be done first and in that order, with the timing of assessments based on collecting the PK sample at the protocolled time.

The investigator or delegate at the site will assess the ECG results. The three QTcF values from a triplicate ECG should be averaged to yield the QTcF value for the purpose of eligibility assessment. The derived variable will be calculated according to the formula of Fridericia using an online calculator.

The overall ECG assessment will be categorized as ‘normal’, ‘abnormal, not clinically significant (NCS)’, or ‘abnormal, clinically significant (CS)’. The overall ECG assessment by the ECG recorder and the related diagnostic comments will not be entered in the eCRF.

Any clinically significant abnormality in the ECG should be investigated by unscheduled ECG assessment(s) (number and timing at investigator's discretion). The confirmed clinically significant abnormalities should be reported as AE in the eCRF.

6.3 Adverse events

The term adverse event is defined as any untoward medical occurrence in a subject or clinical investigation in a subject administered a pharmaceutical product(s) and which does not necessarily have to have a causal relationship with this experimental treatment(s).

An AE is any symptom, physical sign, syndrome, or disease that either emerges during the study or, if present at screening, worsens during the study, regardless of the suspected cause of the event. All AEs that occur in enrolled subjects during the AE reporting period specified in the protocol must be recorded, regardless of the relationship of the AE to study drug.

All medical and psychiatric conditions (except those related to the indication under study) present at screening will be documented on the Medical History CRF page. Clinically significant worsening in these conditions and new symptoms, physical signs, syndromes, or diseases should be noted on the AE eCRF page during the rest of the study. Laboratory, VS, and ECG abnormalities should also be recorded as AEs when considered clinically significant and representing a change from pre-treatment baseline.

Surgical procedures themselves are not AEs; they are therapeutic measures for conditions that require surgery. The condition for which the surgery is required may be an AE. Planned surgical measures for preexisting, non-worsening conditions permitted by the clinical study protocol and the condition(s) leading to these measures are not AEs. Except when the event would qualify as serious (e.g. leading to hospitalization).

Adverse events will be assessed by verbal probes and subject's spontaneous reports at screening and during every post-baseline clinic visit and telephone contact from the start of treatment until the STFU Visit. Information will be collected by trained, qualified study staff and the information will be recorded in the appropriate eCRFs. At a minimum, all relevant information regarding the AE and concomitant medication use will be captured.

All AE reports (solicited or volunteered) will be reviewed and followed by the responsible investigator and medical monitor qualified delegate for completeness, relatedness and accuracy of severity grading in order to ensure appropriate reporting practice. Cumulative AE data will be reviewed periodically by the medical monitor as well as *ad hoc* review of serious and/or severe AEs as they are reported.

Natural disease progression of the malignancy or deterioration of the subject's condition under study (including new sites of metastasis and death due to disease progression) will be recorded as part of the efficacy evaluation and should not be reported as an AE or as an SAE.

Discontinuation from the study treatment because of disease progression or deterioration of the subject's condition of the disease under study should be recorded on the Study Completion page of the eCRF as disease progression and not as an AE.

6.3.1 AE reporting period

The AE reporting period will begin on the day of the first dose of study drug until the STFU call, or until the start of new cancer therapy (unless the investigator believes the AE is related to MT-3724), whichever occurs first.

Grade ≥ 2 AEs related to MT-3724 and/or LEN that were ongoing at the STFU Visit should be followed by the investigator until all events have resolved to Grade ≤ 1 .

Those AEs that occur after the first dose on C1D1 will be considered treatment-emergent.

All AEs that occur in enrolled subjects during the AE reporting period specified in the protocol must be recorded, regardless of the relationship of the AE to MT-3724 or LEN. Any serious known untoward event that occurs beyond the AE reporting period that the investigator assesses as at least possibly related to MT-3724 should also be reported to the sponsor.

For AEs of CLS, CRS/SIRS, and IRRs, individual symptoms and grade should be reported on the appropriate CRF.

6.3.2 Adverse event terminology

All AEs should be recorded in standard medical terminology rather than the subject's own words. Each AE will also be described in terms of duration, frequency, severity/intensity, association with the study medication, assessment of possible causes, actions taken, and outcome, using choices given on the eCRF.

6.3.3 Severity

Severity will be classified according to the criteria provided by CTCAE v5.0. If the AE is not listed in the CTCAE v5.0, then the highest severity level reached according to the scale in Table 8 will be assigned.

Table 8: Classification of Adverse Events by Severity

Grade	Definition
Grade 1 (mild)	An AE that is easily tolerated by the subject. It incurs only a minimum of discomfort and does not influence ordinary daily tasks.
Grade 2 (moderate)	An AE that is of sufficient severity to have a negative influence on ordinary daily tasks.
Grade 3 (severe)	An AE that effectively hinders ordinary daily tasks, often requiring intervention.
Grade 4 (life threatening or disabling)	An AE that puts the subject's life at risk.
Grade 5 (fatal)	Death related to an AE.

AE =adverse event

Every effort should be made to find the appropriate AE term and definitions of severity in the modified CTCAE v. 5.0.

Causality/Relatedness

Causality should be assessed separately for each study drug (MT-3724 and LEN) as detailed in the eCRF. If the investigator feels that the event cannot be firmly attributed to one of the study drugs, then the same assessment should be documented for each study drug. Causal relationship to protocol required procedure(s) should also be considered and reported accordingly in the eCRF.

The following should be considered when assessing causality:

- temporal associations between the agent and the event
- effect of de-challenge and/or re-challenge
- pre-existing risk factors
- a plausible mechanism
- concurrent illnesses.

The investigator will determine the causal relationship/relatedness to the study drug(s) according to the classification in Table 9.

Table 9 Classification of Adverse Events by Causality/Relationship to the Study Drug(s)

Causality/Relatedness	Definition
Definitely related	Follows a reasonable temporal sequence from drug administration, abates upon discontinuation of the drug (de-challenge), is confirmed by reappearance of the reaction on repeat exposure (re-challenge).
Probably related	Follows a reasonable temporal sequence from drug administration, abates upon discontinuation of the drug, cannot be reasonably explained by the known characteristics of the subject's clinical state.
Possibly related	Follows a reasonable temporal sequence from drug administration, could have been produced by the subject's clinical state or by other modes of therapy administered to the subject.
Unlikely to be related	Does not follow a reasonable temporal sequence from drug administration, is readily explained by the subject's clinical state or by other modes of therapy administered to the subject.
Unrelated	The AE is definitely produced by the subject's clinical state or by other modes of therapy administered to the subject.

AE = adverse event

For all purposes of subject management, DLT assignment and treatment modification, the causality assessment of:

- “probably”, “possibly” or “definitely” will be treated as “related”
- “unlikely” and “not related” will be treated as “unrelated”

6.3.4 Expected and unexpected adverse events and SUSARs

The expectedness of AEs will be determined by the sponsor according to the applicable reference document(s) and the requirements of the health authorities.

An **unexpected** AE is an AE that is not identified by type, severity grade, or frequency in the Reference Safety Information (RSI) section of the IB for MT-3724 or in the MT-3724 safety reports to the health authorities (e.g. development safety update report) and for LEN any ADR that is not described in the **Revlimid®** reference prescribing information.

The Safety Department of the Contract Research Organization (CRO) must report any suspected, unexpected serious adverse reaction (SUSAR) to the regulatory authorities within the required timeframes. The investigator must report any SUSARs to the Institutional Review Boards (IRBs)/Independent Ethics Committees (IECs) in accordance with local requirements.

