The event must be recorded on the electronic SAE CRF page. Preliminary reports of SAEs must be followed by detailed descriptions later, including clear copies of hospital case reports, consultant reports, autopsy reports, and other documents when requested and applicable. All copies should be redacted to remove subjects' personal details and annotated with the subject's unique study identifiers.

Appropriate remedial measures should be taken to treat the SAE, and the response to treatment should be recorded. Subjects must be closely followed until sufficient information is obtained to indicate a return to normal status or until the event stabilizes at a level acceptable to the investigator. Clinical, laboratory, and diagnostic measures should be employed as needed in order to determine the etiology of the problem. The results will be reported promptly to the sponsor.

Pregnancy reporting instructions

Pregnancy should be avoided from 4 weeks prior to first dose of LEN, during treatment, during dose interruptions and for 4 weeks following the last dose of LEN or MT-3724. Reliable contraception is specified in the exclusion criteria, see [Section 4.2](#).

Subjects must be advised to immediately notify the investigator of pregnancy.

If pregnancy occurs during treatment in a subject, the investigator must immediately discontinue the study drugs (MT-3724 and LEN) and report the pregnancy to the Safety Department of the CRO and the medical monitor (See List of Contacts), along the same timelines as an SAE ([Section 6.3.5](#)). The subject must be referred to an obstetrician/gynecologist experienced in reproductive toxicity for further evaluation and counseling.

The investigator maintains the responsibility for reporting pregnancy in accordance with the Revlimid REMS program ([REVLYMID REMS®](#)).

For a study subject, the outcome of the pregnancy should be followed up carefully, and any abnormal outcome of the mother or the child should be reported. For the pregnancy of a study subject's partner, all efforts should be made to obtain similar information on course and outcome, subject to the partner's consent.

Suspected Unexpected Serious Adverse Reaction

An unexpected SAE that is at least possibly related to the study drug will be considered a Suspected Unexpected Serious Adverse Reaction (SUSAR). Please see [Section 6.3.4](#) for the definition of the unexpected event.

The sponsor will determine if a reported SAE meets the criteria for SUSAR.

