7.13 Interim analysis

No formal interim statistical analysis is planned during either part of this study. A formal interim statistical analysis may be performed only pursuant to a health authority request.

Informal (preliminary) statistical analyses may be performed at sponsor's discretion at any time during the study. These analyses would be performed without the interim data base lock for the purposes of the IB update, safety reports to the health authorities (e.g., data safety update report), meetings with health authorities or for internal decisions.

In addition, data from individual subjects and cohorts will be reviewed without formal statistical analysis on an ongoing basis during the study (e.g. to support the dose escalation decisions in Part 1).

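### Section 6.3.4 lets past safety reports to authorities, as well as the RSI, make an MT-3724 reaction expected, so later matching cases can fall outside SUSAR reporting

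*Protocol*

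**What the plan says.** Protocol Section 6.3.4 opens with a general rule: "The expectedness of AEs will be determined by the sponsor according to the applicable reference document(s) and the requirements of the health authorities". It then defines an unexpected event. For MT-3724 this is one "not identified by type, severity grade, or frequency in the Reference Safety Information (RSI) section of the IB for MT-3724", and the sentence continues "or in the MT-3724 safety reports to the health authorities (e.g. development safety update report". For lenalidomide the same sentence uses a single reference, the prescribing information: "and for LEN any ADR that is not described in the" Revlimid label.

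The section then requires that the CRO's safety department "must report any suspected, unexpected serious adverse reaction (SUSAR) to the regulatory authorities within the required timeframes", and that investigators report SUSARs to IRBs/IECs under local requirements. Section 6.3.5 supplies the link: "An unexpected SAE that is at least possibly related to the study drug will be considered a Suspected Unexpected Serious Adverse Reaction". For the meaning of unexpected, it sends the reader back to Section 6.3.4.

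The SAP has no rule on expectedness or SUSARs, so it neither resolves nor contradicts the protocol.

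**The concern.** The definition gives MT-3724 two alternative references. An event found in either one is not unexpected. The second reference is not the RSI but the sponsor's own past reporting. A reaction can therefore become expected because it has been reported, without any decision to add it to the RSI.

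What is at stake is notification outside the sponsor and the sites. The trial is open-label, and the sponsor makes the dose and MTD decisions with the investigators (Sections 3.6 and 3.6.3). SUSAR reporting is one of the routes by which regulators and ethics committees learn of a new serious reaction and its recurrence. The clause is not limited to this study. Section 1.2.1 lists three ongoing MT-3724 studies, one of them monotherapy, and a report arising from any of them could count here.

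**Working it through.** The plan states no figure that depends on this definition, so the check is one of reading the sections together.

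**Step 1: the chain.** Under 6.3.5 a SUSAR must be serious, at least possibly related, and unexpected. Unexpected is defined in 6.3.4. The duties in 6.3.4 towards regulators and IRBs/IECs are written for SUSARs. Whatever makes a reaction expected under 6.3.4 therefore takes it out of those duties.

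**Step 2: the two references.** I read the sentence in its ordinary sense: an event is unexpected only if it is found in neither reference. A reaction absent from the RSI but identified in a qualifying safety report is then expected. Lenalidomide has no such second reference, so the effect is confined to the investigational drug.

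**Step 3: which reports qualify.** The text does not define the term. Its only example is a periodic report. Section 7.13 uses the same phrase, again with a periodic example: "safety reports to the health authorities (e.g., data safety update report". SAP Section 9 does likewise, naming the DSUR.

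| Reading of safety reports | When a matching later case can become expected |
|---|---|
| Periodic reports only | Once a periodic report containing the reaction is submitted |
| Periodic and single-case reports | From the first single-case report onwards |

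Both rows end in the same place: the reaction can be expected while the RSI still omits it. They differ only in when that starts.

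**Step 4: what counts as matching.** The comparison is on type, severity grade or frequency, not on mere mention. The sentence can be taken in two ways. If a mismatch on any one attribute is enough, a case of higher grade or a rise in frequency is still unexpected, and only cases alike on all three are lost. If an event is unexpected only when none of the three is identified, more cases are lost. The wording does not settle which applies.

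**Step 5: is there time for this to happen?** The reference list cites IB version 5.0, effective 20 November 2019, while Section 1.2.1 gives programme safety data as of 18 March 2020. Information does accrue between IB versions. This does not show that an unlisted serious reaction was in any report, only that a gap between reporting and updating is realistic.

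**Step 6: what does not depend on expectedness.** Sites report every SAE within 24 hours, whatever its cause (6.3.5). Escalation rests on DLTs and on all available cohort data (3.6), with possible DLTs followed in real time (3.6.4). None of these steps uses the definition.

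**The case against.** The strongest defence is that other text governs. Expectedness must also follow health authority requirements (6.3.4). The study is to comply with the EU directive, the FDA regulations and ICH (8.1.1). Section 8.1.2 separately has reportable adverse events go to the IRB/IEC under ICH guidelines and local standards, without reference to the 6.3.4 definition. A careful sponsor would probably apply those rules. This stands as mitigation: loss of SUSAR status is possible, not automatic. It does not remove the explicit definition that follows, to which 6.3.5 refers the reader. The section then contains two rules that can conflict.

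A reader might go further and infer that the first SUSAR report makes the next case of the same reaction non-expedited. The documents do not support that as a statement of fact. It needs single-case reports to count as safety reports, and every example given is periodic. Nor does any mention in a report suffice, since type, grade or frequency must be compared.

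A reader might also infer that dose escalation loses a safeguard. It does not, for the reasons in the last step of the check. The reply that these internal steps therefore close the gap also fails, because they reach the sponsor, its CRO, the medical monitor and the investigators. DLT rules also apply only to Part 1, while Part 2 may treat up to 40 subjects.

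Finally, an event attributed to both drugs might be thought to become expected because one drug's reference lists it. Section 6.3.4 gives each drug its own reference and says nothing of the kind. Section 6.3.3 asks for causality by drug and says only what to record when attribution is unclear. It does not suggest that this is frequent. Only a clarification is warranted.

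**Conclusion.** The point holds in a limited form. As written, a serious related MT-3724 reaction that the RSI does not list can lose SUSAR status because it was already identified in a safety report. Later matching cases would then not go to regulators on the SUSAR timeline or to IRBs/IECs as SUSARs. The exposure runs from submission of a qualifying report until the RSI lists the reaction.

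The size cannot be stated as a number. It is zero if no unlisted serious reaction recurs in that interval. Otherwise it depends on counts and report dates that the documents do not give.

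The conclusion rests on two assumptions: that the two references are alternatives, as the sentence ordinarily reads, and that the explicit definition is applied rather than overridden by the general appeal to health authority requirements. It does not depend on whether single-case reports count. The definition should be corrected because the change is cheap and protects reporting outside the sponsor. It does not call the dose-escalation rules or any planned analysis into question.

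**What to change.** In Section 6.3.4, delete "or in the MT-3724 safety reports to the health authorities (e.g. development safety update report" together with its closing bracket, so that MT-3724 expectedness is judged against the RSI alone. In the same sentence, state that a mismatch with the RSI in type, in severity grade or in frequency is each enough to make an event unexpected. Possible wording: *An MT-3724 event is unexpected if its type, its severity grade or its frequency is not consistent with the RSI section of the IB; a difference in any one of these is sufficient.*

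As a clarification only, add that an event possibly related to both drugs is judged separately against each drug's reference document.

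The cost is a sentence or two in the protocol and alignment of any safety-reporting procedure that repeats the definition. The SAP needs no change. The downside is somewhat more expedited reports, since recurrences of a known but unlisted reaction would continue to be sent until the RSI is updated.
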